10.2. Trial entry and enrollment: Medication schedule

Study drug will be administrated twice a day during days 1 and 2. Patients will be monitored for adverse events.

10.2.1. Clinical and laboratory follow up:

Subjects will be followed through regularly scheduled visits that will include: vital signs, physical examination, ongoing medical history review, and laboratory tests as described in Table 5.

Safety will be assessed by monitoring the subjects for AEs. The subjects will be instructed as to what is an AE and will be requested to fill out a diary detailing any AEs that may occur during the time period between visits.

Evaluation of the effect of oral administration of the study drug will be assessed by determining the clinical and laboratory tests as summarized below.

	MGC Pharma Clinical Study Protocol	Protocol No.: MGC-009
		Version 02, 05 Sep 2021
		Page 38 of 76
A Phase IIb, double blind, placebo-controlled clinical study designed to evaluate the effect of CimetrA in patients diagnosed with COVID-19		CONFIDENTIAL

Table 5: Schedule of events

Day	1	2	3-6	7	8-13	14	Day 21(phone visit)	Day 28 Clinic visit
Confirmed SARS-CoV-2 infection	X					X		X
Treatment administration (twice a day)	X	X						
Inclusion/Exclusion criteria evaluation	X							
Informed Consent	X							
Medical History	X							
Concomitant Medications	X	X	X	X	X	X	X	X
AE Assessment		X	X	X	X	X	X	X
Randomization	X							
Physical Examination	X	X	X	X	X	X		X
Vital Signs	X	X	X	X	X	X		X
Hematology blood test (local)	X	X	X**	X	X**	X		X
Biochemistry blood test (local)	X	X	X**	X	X**	X		X
WHO Ordinal Score	X			X		X	X	X
COVID-19-Related Symptoms assessment	X			X		X	X	X
PK test*	X							
Blood test for inflammatory markers (IL-6, IL-1 β , IL-12, TNF α , IFN- γ) (local)	X	X	X	X		X		X

	MGC Pharma Clinical Study Protocol	Protocol No.: MGC-009
		Version 02, 05 Sep 2021
		Page 39 of 76
A Phase IIb, double blind, placebo-controlled clinical study designed to evaluate the effect of Cimetra in patients diagnosed with COVID-19		CONFIDENTIAL

D-Dimer test (local)	X	X		X		X		X
VAS scale	X	X	X	X	X	X	X	X
Urine pregnancy test for women of childbearing potential	X							X
ECG	X							x
COVID-19–Impact on Quality of Life Questionnaire	X			X	X	X	X	X
POST- COVID-19 Functional Status Scale								X

Biochemistry blood test: Sodium (Na), Potassium (K), Chloride (Cl), Creatinine, Glucose, Urea, Albumin, Calcium total, Alkaline Phosphatase (ALP), ALT, AST, Total Bilirubin, Direct Bilirubin, LDH, Total Protein, Uric Acid, CRP, and Lipid Profile (including Total Cholesterol, HDL, LDL, Triglycerides).

Hematology blood test: complete CBC.

D-Dimer test (coagulation): one tube for coagulation test

Inflammatory markers: the blood will be centrifuged and frozen according to the Lab manual, Local Lab.

Vital signs: blood pressure, pulse, weight, weight, body temperature (PO), saturation, respiratory rate.

VAS scale: will be performed by study staff member.

WHO Ordinal Score: will be completed by the study staff member based on patient status.

COVID-19-Related Symptoms assessment: will be completed by the study staff member based on patient status and answers.

COVID-19–Impact on Quality-of-Life Questionnaire: will be completed by the study staff member based on patient answers.

	MGC Pharma Clinical Study Protocol	Protocol No.: MGC-009
		Version 02, 05 Sep 2021
		Page 40 of 76
A Phase IIb, double blind, placebo-controlled clinical study designed to evaluate the effect of CimetrA in patients diagnosed with COVID-19		CONFIDENTIAL

POST- COVID-19 Functional Status Scale: will be completed by the study staff member based on patient answers.

Pregnancy test: women of childbearing potential must undergo a urine pregnancy test.

Physical examination: full examination by doctor.

** Measurements will be performed per institutional schedule by the hospital staff, not necessarily by the principal investigator or the sub-investigators.

PK parameters*: will be performed only on 14 patients that will agree to participate in the PK analysis (only for Brazil and South Africa).

The PK will be performed only for the first dose of drug, after patient received the first dose (5 puffs) the study staff need to follow the table below.

For each test, approximately 5 ml of blood will be drawn (equivalent to one teaspoon) total of 55 ml of blood will be drawn.

Table 6: List of time points for pharmacokinetic assessments

Study Visit Number 1	
Time point 0	Dosing (before the first dose of the drug)
Time Point 1	15 minutes post dose
Time Point 2	30 minutes post dose
Time point 3	45 minutes post dose
Time point 4	1 h post dose
Time point 5	1.5 h post dose
Time point 6	2 h post dose
Time point 7	4 h post dose
Time point 8	6 h post dose
Time point 9	8 h post dose
Time point 10	10 h post dose

	MGC Pharma Clinical Study Protocol	Protocol No.: MGC-009
		Version 02, 05 Sep 2021
		Page 41 of 76
A Phase IIb, double blind, placebo-controlled clinical study designed to evaluate the effect of Cimetra in patients diagnosed with COVID-19		CONFIDENTIAL

Time point 11	12 h post dose
---------------	----------------

Day 1

Prior to engaging in any study procedures, the subject must meet the inclusion/exclusion criteria by history (which includes a signed declination), and review and sign an ICF.

Following procedures will be performed during the visit –

- Inclusion/Exclusion criteria evaluation
- Informed Consent
- Medical History
- Concomitant Medications
- Physical Examination
- Vital Signs
- Hematology blood test (local, mandatory even if there are available results from the day before)
- Biochemistry blood test (local, mandatory even if there are available results from the day before)
- PCR test for detection COVID-19 (within 5 days from admission to hospital)
- COVID-19-Related Symptoms Assessment
- WHO Ordinal scale
- Blood test for inflammatory markers (IL-6, IL-1 β , IL-12, TNF α , IFN- γ) (local)
- D-Dimer test (local)
- VAS scale
- Urine pregnancy test for women of childbearing potential
- ECG
- COVID-19–Impact on Quality of Life Questionnaire

	MGC Pharma Clinical Study Protocol	Protocol No.: MGC-009
		Version 02, 05 Sep 2021
		Page 42 of 76
A Phase IIb, double blind, placebo-controlled clinical study designed to evaluate the effect of CimetrA in patients diagnosed with COVID-19		CONFIDENTIAL

- Randomization in 1:1:1 ratio to study drug (CimetrA-1) (Arm 1) or study drug (CimetrA-2) or to Placebo (Arm 3)
- Treatment administration (twice a day, morning, and evening)
- **PK test (only for Brazil and South Africa)** for first dose of the drug (5 puffs) as the table on page 36, PK must be done **before** receiving standard of care.

Day 2

- Concomitant Medications
- AE Assessment
- Physical Examination
- Vital Signs
- Hematology blood test (local, mandatory even if there are available results from the day before)
- Biochemistry blood test (local, mandatory even if there are available results from the day before)
- Blood test for inflammatory markers (IL-6, IL-1 β , IL-12, TNF α , IFN- γ) (local)
- D-Dimer test (local)
- VAS scale
- Treatment administration (twice a day, morning and evening)

Days 3-6

- Concomitant Medications
- AE assessment
- Physical Examination
- Vital Signs
- Hematology blood test **

	MGC Pharma Clinical Study Protocol	Protocol No.: MGC-009
		Version 02, 05 Sep 2021
		Page 43 of 76
A Phase IIb, double blind, placebo-controlled clinical study designed to evaluate the effect of Cimetra in patients diagnosed with COVID-19		CONFIDENTIAL

- Biochemistry blood test **
- Blood test for inflammatory markers (IL-6, IL-1 β , IL-12, TNF α , IFN- γ) (local)
- VAS scale

Day 7

- Concomitant Medications
- AE assessment
- Physical Examination
- Vital Signs
- Hematology blood test (local, mandatory even if there are available results from the day before)
- Biochemistry blood test (local, mandatory even if there are available results from the day before)
- WHO Ordinal Score
- COVID-19-Related Symptoms assessment
- Blood test for inflammatory markers (IL-6, IL-1 β , IL-12, TNF α , IFN- γ) (local)
- D-Dimer test (local)
- VAS scale
- COVID-19–Impact on Quality of Life Questionnaire

Days 8-13

- Concomitant Medications
- AE assessment
- Physical Examination
- Vital Signs

	MGC Pharma Clinical Study Protocol	Protocol No.: MGC-009
		Version 02, 05 Sep 2021
		Page 44 of 76
A Phase IIb, double blind, placebo-controlled clinical study designed to evaluate the effect of CimetrA in patients diagnosed with COVID-19		CONFIDENTIAL

- Hematology blood test **
- Biochemistry blood test **
- VAS scale

Day 14

- Concomitant Medications
- AE assessment
- Physical Examination
- Vital Signs
- Hematology blood test (local, mandatory even if there are available results from the day before)
- Biochemistry blood test (local, mandatory even if there are available results from the day before)
- WHO Ordinal Score
- COVID-19-Related Symptoms assessment
- Blood test for inflammatory markers (IL-6, IL-1 β , IL-12, TNF α , IFN- γ) (local)
- D-Dimer test (local)
- VAS scale
- PCR test for detection COVID-19
- COVID-19–Impact on Quality of Life Questionnaire

Day 21 (phone visit)

- Concomitant Medications
- AE assessment
- VAS scale
- COVID-19–Impact on Quality of Life Questionnaire WHO Ordinal Score

	MGC Pharma Clinical Study Protocol	Protocol No.: MGC-009
		Version 02, 05 Sep 2021
		Page 45 of 76
A Phase IIb, double blind, placebo-controlled clinical study designed to evaluate the effect of CimetrA in patients diagnosed with COVID-19		CONFIDENTIAL

- COVID-19-Related Symptoms assessment

Day 28 – Follow Up (clinic visit)

- Concomitant Medications
- AE assessment
- Physical Examination
- Vital Signs
- Hematology blood test (local, mandatory even if there are available results from the day before)
- Biochemistry blood test (local, mandatory even if there are available results from the day before)
- WHO Ordinal Score
- COVID-19-Related Symptoms assessment
- Blood test for inflammatory markers (IL-6, IL-1 β , IL-12, TNF α , IFN- γ) (local)
- D-Dimer test (local)
- VAS scale
- PCR test for detection COVID-19
- Urine pregnancy test for women of childbearing potential
- ECG
- COVID-19–Impact on Quality of Life Questionnaire
- POST- COVID-19 Functional Status Scale

In case of **hospital discharge** within the study period, follow up will continue per protocol until day 28 wherever the subject will be located, depending on the status of the patient and study schedule.

	MGC Pharma Clinical Study Protocol	Protocol No.: MGC-009
		Version 02, 05 Sep 2021
		Page 46 of 76
A Phase IIb, double blind, placebo-controlled clinical study designed to evaluate the effect of CimetrA in patients diagnosed with COVID-19		CONFIDENTIAL

If patient discharged, visits will be performed via phone call, if he still hospitalized, visits will be performed at corona department.

Only on day 28, all the patients must undergo clinic visit , they will arrive to the research clinic.(only patient who will be under quarantine will have a phone call visit.)

11. STUDY POPULATION

11.1. Inclusion Criteria:

1. Confirmed by PCR test SARS-CoV-2 infection (according to nationally authorized laboratory criteria).
2. Hospitalized patient with COVID-19 of moderate stable or worsening severity not requiring ICU admission (defined by NIH criteria - fever, cough, dyspnea, fast breathing, but no signs of severe pneumonia, including SpO₂ ≥ 94% on room air).
3. Age: 18 years old and above.
4. Subjects must be hospitalized
5. Ability to receive treatment by spray into the oral cavity

	MGC Pharma Clinical Study Protocol	Protocol No.: MGC-009
		Version 02, 05 Sep 2021
		Page 47 of 76
A Phase IIb, double blind, placebo-controlled clinical study designed to evaluate the effect of CimetrA in patients diagnosed with COVID-19		CONFIDENTIAL

11.2. Exclusion Criteria:

1. Tube feeding or parenteral nutrition.
2. Patients with scores 5 or above per the Ordinal Scale for Clinical Improvement published by the WHO. (i.e., who need oxygen supply beyond use of nozzles or simple mask)
3. Need for admission to ICU while of the present hospitalization at any time prior to completion of the recruitment to the study.
4. Any condition which, in the opinion of the Principal Investigator, would prevent full participation in this trial or would interfere with the evaluation of the trial endpoints.

11.3. Removal of subjects from therapy or assessment

- a. If any of the inclusion criteria fails to be met, or any of the exclusion criteria is met during the period in which the interim history, physical examination and laboratory tests are performed, the subject will be ineligible to continue in the study. These subjects will be classified as screened but not enrolled.
- b. If the subject begins a regimen of medication at any time during the study that includes any of the medications listed in the exclusion criteria or begins an increase in dose of an existing regimen of medication at any time during the study, the subject will be terminated from the study. These subjects will not be used in the primary analyses.
- c. If continuing in the study does not appear to be in the best medical interest of the subject, his/her participation may be terminated by either the Principal

	MGC Pharma Clinical Study Protocol	Protocol No.: MGC-009
		Version 02, 05 Sep 2021
		Page 48 of 76
A Phase IIb, double blind, placebo-controlled clinical study designed to evaluate the effect of CimetrA in patients diagnosed with COVID-19		CONFIDENTIAL

Investigator or the study director. Removal of an individual by the Principal Investigator will be reported to the Institutional Helsinki Committee and the appropriate regulatory agencies according to the guidelines of these groups. These subjects will not be used in the primary analyses unless the reason for removal was due to reasons of safety in which case data would be used in the primary analyses.

d. In addition to a participant being able to voluntarily withdraw from the study at any time, the Investigator may withdraw participants from the study under the conditions noted below, and such subjects will not used in the primary analyses.

e. Participants will be withdrawn from the treatment protocol if participants are unwilling or unable to comply with the schedule of treatment, follow-up or safety monitoring, and will not be used in the primary analyses.

f. Subjects considered treatment failures will be removed from the study and will be offered alternative standard therapy by their treating physician and will not be used in the primary analyses.

11.4. **Screening and Enrollment logs**

A screening log of subjects who are screened but not enrolled will be kept by the site. The reason(s) for not enrolling a subject should be stated in each case. An enrollment log of subjects who did not meet eligibility criteria at Randomization will also be kept by the clinic. The reason(s) for not including a subject should be stated in each case.

12. **STUDY TREATMENT**

	MGC Pharma Clinical Study Protocol	Protocol No.: MGC-009
		Version 02, 05 Sep 2021
		Page 49 of 76
A Phase IIb, double blind, placebo-controlled clinical study designed to evaluate the effect of CimetrA in patients diagnosed with COVID-19		CONFIDENTIAL

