13. **CONCOMITANT MEDICATIONS DURING THE STUDY**

13.1. **General guidelines**

All prior treatments received by the subject within 60 days of the initial screening visit will be recorded on the subject's CRF including the treatment's name, indication and the start and stop dates.

All concomitant medications taken by the subject (including prescription, over-the-counter, herbal supplements and health store products) must be recorded on the CRF, along with the indication and start and stop dates as well as daily dose.

13.2. **Allowed Concomitant Medications/Therapies during Study**

Concomitant medications allowed to be used in this study are those used at screening to control existing medical condition and/or those taken during the study to treat possible adverse events. All concomitant medications used to treat adverse events will be recorded in the subject's medical file and on the appropriate CRF page.

If intake of a drug should become necessary for any reason during the course of the study, the subject is required to inform the Investigator immediately, who will record the drug, the dose and the time of administration in the subject's CRF.

Standard of care treatment acceptable to be used while patient participates in study :

Treatment will include:

Supportive care - symptomatic

Painkillers

Anticoagulant therapy

Steroids

	MGC Pharma Clinical Study Protocol	Protocol No.: MGC-009
		Version 02, 05 Sep 2021
		Page 54 of 76
A Phase IIb, double blind, placebo-controlled clinical study designed to evaluate the effect of CimetrA in patients diagnosed with COVID-19		CONFIDENTIAL

REMEDSIVIR - Compassionate treatment

Antibiotic treatment as needed

Inhalations if necessary

Oxygen

The treatments offered above are given according to the guidelines of the Ministry of Health.

The treatment will be given to the patient according to the clinical judgment of the medical staff and in accordance with the patient's health condition, and therefore the treatment does not have to be the same in each of the medical centers participating in the study.

13.3. **Potential Adverse Events and risks for the patient in the study**

During Phase II study on 50 COVID-19 patients no drug related adverse events were reported. The full safety profile is presented above .

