17. STATISTICAL METHODS AND DETERMINATION OF SAMPLE SIZE

A prospective, randomized (1:1:1), double-blind, multi-center, placebo-controlled clinical study.

Statistical Hypothesis

The hypothesis of this study is that treating with CimetrA and CimetrA2 will be more effective, while maintaining a favorable safety profile. This will be demonstrated by a significant difference between the two active and the control groups.

	MGC Pharma Clinical Study Protocol	Protocol No.: MGC-009
		Version 02, 05 Sep 2021
		Page 60 of 76
A Phase IIb, double blind, placebo-controlled clinical study designed to evaluate the effect of Cimetra in patients diagnosed with COVID-19		CONFIDENTIAL

In this study, we will test the following hypothesis:

- H0: $\Delta_1 = \Delta_2 = \Delta_3$
- H1: at least one is different.

Where Delta is the difference between baseline and end of study in WHO Ordinal Scale for clinical trial.

If the null hypothesis is rejected in favor of the alternative hypothesis the study will be deemed successful.

Safety will be assessed by adverse events, blood and urine laboratory assessments and vital signs.

Planned Sample Size

For this phase IIb, 3-armed clinical trial, we use the ANOVA test to estimate the expected improvement in the primary outcome; the WHO ordinal scale for clinical improvement.

We expect medium effect ($f=0.20$) for the differences in Delta between the 3 groups, and standard deviation of 1.5, based on the ordinal scale (0-8). This power analysis is for a one-way fixed effects analysis of variance with 3 levels. The study will include 80 patients per group for a total of 240 patients.

The criterion for significance (α) has been set at 0.05 with Power of at least 80%.

The analysis of variance is two-tailed Main effects.

For immunogenicity assessment, larger sample size will reduce mean variability in the observed outcomes and will increase the opportunity to detect real changes.

For 80 participants per group we ensure the desired precision for phase 3 trial to assess safety and effectiveness. Total sample 240 patients.

Computer Software

	MGC Pharma Clinical Study Protocol	Protocol No.: MGC-009
		Version 02, 05 Sep 2021
		Page 61 of 76
A Phase IIb, double blind, placebo-controlled clinical study designed to evaluate the effect of CimetrA in patients diagnosed with COVID-19		CONFIDENTIAL

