The overall significance level for this study is 5% using two-tailed tests, except for treatment by center/region interaction that will be tested at a significance level of 10%.

When multiple comparisons between the groups are made, the chance of finding a significant difference in one of the comparisons is greater than the stated significance level, therefore we will use pot-hoc analysis.

Efficacy endpoints:

Time to sustained clinical improvement (as defined earlier).

Safety Endpoints

The safety endpoints of adverse events and tolerability will be assessed by review of all safety parameters, including adverse events.

	MGC Pharma Clinical Study Protocol	Protocol No.: MGC-009
		Version 02, 05 Sep 2021
		Page 63 of 76
A Phase IIb, double blind, placebo-controlled clinical study designed to evaluate the effect of CimetrA in patients diagnosed with COVID-19		CONFIDENTIAL

The incidence of adverse events will be assessed as a function of severity and association to the device. The time of resolution of the adverse events and need for treatment will also be analyzed.

Analysis Sets

The ITT analysis set will serve as the main set for safety assessments.

The primary and secondary performance efficacy assessments will also be performed on the PP and the ITT analysis sets.

Statistical Analysis

Demographic and Baseline

Demographic and baseline condition related characteristics will be tabulated and compared between the study arms by data type. Continuous variables will be summarized by a mean, standard deviation, minimum, median and maximum and categorical variables by a count and percentage.

Primary Efficacy Analysis

The primary efficacy endpoint of the study is the mean change in the WHO Ordinal Scale. It will be evaluated using a General Linear Model ANOVA test.

Subset Analyses

The primary endpoint will also be evaluated stratified by center using a General Linear Model ANOVA test.

A sensitivity analysis of the primary endpoint will be performed to assess the impact of missing data on the study outcome.

Adjustment for other covariates such as demographics or other baseline participant characteristics may be performed by adding these variables into a multivariate linear regression.

Secondary Efficacy Analysis

	MGC Pharma Clinical Study Protocol	Protocol No.: MGC-009
		Version 02, 05 Sep 2021
		Page 64 of 76

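### Section 11.3 drops randomised patients from the primary analyses for post-randomisation events, including undefined treatment failure, and the ITT wording in Section 17 contradicts this without overriding it

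*Protocol*

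**What the plan says.** Protocol Section 11.3 lists who leaves the study and what happens to their data.

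- **Item b:** a patient who starts a medication named in the exclusion criteria, or who "begins an increase in dose of an existing regimen of medication at any time during the study", is terminated from the study and left out of the primary analyses.
- **Item c:** a patient removed in his or her best medical interest is left out, unless the reason was safety.
- **Items d and e:** patients withdrawn by the investigator, and those who will not or cannot keep to treatment, follow-up or safety monitoring, are left out.
- **Item f:** "Subjects considered treatment failures will be removed from the study and will be offered alternative standard therapy by their treating physician". The sentence closes with "by their treating physician and will not be used in the primary analyses". No definition of treatment failure is given.

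Section 17 reads differently. Under Missing Data, missing values are to be handled as ITT. Last observation carried forward applies to patients with no post-baseline measurement and to withdrawals for an adverse event or intolerability. Under Analysis Sets, ITT is the main set for safety, and "The primary and secondary performance efficacy assessments will also be performed on the PP and the ITT analysis sets". Nothing there withdraws the exclusions in 11.3.

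The primary efficacy variable in Section 17 is the change from baseline to end of study on the WHO ordinal scale. In Section 9.1 that scale runs up to high-flow oxygen or NIV (5), ventilation (6 and 7) and death (8).

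**The concern.** Randomisation protects the comparison only while patients are analysed whatever happens to them afterwards. Each exclusion in 11.3 b to f turns on something that can occur after randomisation and may depend on the course of the disease or on the treatment.

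Item f matters most. Eligible patients score below 5 (exclusion criterion 2), and Section 12.1 gives prevention of deterioration as part of the rationale for the drug. A patient judged a treatment failure is therefore likely to be moving up the very scale that the trial measures. If such patients leave the analysis, a real effect on deterioration can vanish from the primary comparison. If they are removed more readily in one arm than another, a difference can appear where none exists. Because the term is undefined, its use may vary between sites.

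Data collection is also at stake. Dosing ends on Day 2, so removal from the study after that point mainly stops observation.

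**Working it through.** **1. The plan's own figure.** The inputs are in Section 17: "We expect medium effect ($f=0.20$) for the differences in Delta between the 3 groups", "standard deviation of 1.5, based on the ordinal scale (0-8"), a significance level that "has been set at 0.05 with Power of at least 80" percent, and 80 patients per arm. For a one-way ANOVA with three groups, the noncentrality is N × f² = 240 × 0.04 = 9.6 on 2 and 237 degrees of freedom. The noncentral F distribution gives a power of 79.3%. The stated 80% is reproduced within rounding. Strictly it is 0.7 points short, and 80% would need 82 per arm (246). Section 17 states no allowance for removals.

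**2. Power if patients are removed, with f held at 0.20.** The removal rates are assumptions, because the protocol gives none.

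| Removed | Per arm | N × f² | Power |
|---|---|---|---|
| 0% | 80 | 9.60 | 79.3% |
| 5% | 76 | 9.12 | 77.1% |
| 10% | 72 | 8.64 | 74.6% |
| 20% | 64 | 7.68 | 69.1% |
| 30% | 56 | 6.72 | 62.8% |

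**3. Hiding an effect.** Assume that failures change by +3 points and all others by -2.5 (negative is improvement), with failure in 15% on placebo and 8% on active.

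- Active: 0.08 × 3 - 0.92 × 2.5 = -2.060
- Placebo: 0.15 × 3 - 0.85 × 2.5 = -1.675
- Difference with everyone kept: -0.385
- Half the failures deleted in each arm: the remaining failure shares are 0.04/0.96 = 4.17% and 0.075/0.925 = 8.11%, so the difference is 5.5 × (0.0417 - 0.0811) = -0.217
- All failures deleted: -2.5 in both arms, so the difference is 0

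The full difference is 5.5 times the gap in failure rates: 0.165 for a gap of 3 percentage points, 0.385 for 7 and 0.825 for 15.

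**4. Hiding or creating an effect, by simulation.** Each setting used 4,000 trials of 80 per arm. Non-failures improve by a mean of 2 points and failures worsen by a mean of 3, with SD 1 around each mean. All are assumptions.

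| Failure rate (active, active, placebo) | Failures deleted | Active-placebo difference | ANOVA rejects |
|---|---|---|---|
| 5%, 5%, 20% | none | 0.75 | 76% |
| 5%, 5%, 20% | all | 0.00 | 5% |
| 10%, 10%, 20% | none | 0.50 | 35% |
| 10%, 10%, 20% | all | 0.00 | 5% |
| 15% in each arm | 60% in each arm | 0.00 | 4.8% |
| 15% in each arm | 80%, 80%, 40% | 0.31 | 22% |

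The last row has no true effect. The arithmetic agrees: the remaining failure shares are 0.03/0.88 = 3.4% and 0.09/0.94 = 9.6%, and 5 × (0.0957 - 0.0341) = 0.31.

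**5. Whether Section 17 repairs it.** Table 5 schedules the WHO score on Days 1, 7, 14, 21 and 28. A patient removed as a failure on Day 4 has no post-baseline score. Under the Section 17 rule the Day 1 score is carried forward, and the deterioration is recorded as no change. Such a patient counted under ITT would still contribute a value from before the event.

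**6. Item b against the rest of the protocol.** Section 11.2 lists no medications, so the first clause of item b points to nothing. The dose-increase clause stands beside Sections 10 and 13.2, which allow steroids, anticoagulants and other care by clinical judgment, and "those taken during the study to treat possible adverse events". Raising the dose of an allowed medicine is thus both permitted and a ground for termination.

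**The case against.** Section 17 plans efficacy on the ITT set as well as the PP set, adds a missing-data sensitivity analysis, and asks for safety data from withdrawn patients. An imputed ITT analysis can be run beside 11.3. This stands, and it limits the point: a reader might infer that 11.3 makes ITT impossible, and the documents do not support that. What remains is a contradiction over who belongs in the primary analysis. Only 11.3 says who is left out of it.

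A reader might also infer that every bad outcome is deleted or that harm is concealed. Neither follows. Death is not a removal category, item c keeps removals made for safety, non-compliance is not itself a bad outcome, and no text equates treatment failure with given WHO scores. Safety is analysed on ITT, and ventilation and ICU stay are separate secondary outcomes. At most, harm could be missed in the primary efficacy comparison.

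The illustration is open to challenge too. The fall to 0 is built in, because every failure is deleted and the other patients are identical across arms. The two-point mixture has an SD of 5.5 × √(0.15 × 0.85) = 1.96 on placebo and 5.5 × √(0.08 × 0.92) = 1.49 on active, which does not match a common SD of 1.5. The power table holds f at 0.20 and so describes a different situation from one in which deletion removes the difference. These objections stand: the figures show a mechanism and are not estimates.

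Lastly, newly starting a steroid, an anticoagulant or remdesivir does not trigger item b. The conflict is confined to dose increases of an existing regimen.

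**Conclusion.** The point holds. As written, Section 11.3 b to f removes randomised patients from the primary analyses for events after randomisation, and Section 17 contradicts this without overriding it. The primary WHO-scale comparison can be biased. Towards no difference is the likely direction if the drug prevents failures and those failures are deleted; either direction is possible if removal differs by arm. The documents do not settle which, or by how much.

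On the assumed figures, a difference of -0.385 shrinks to -0.217 when half the failures are deleted and to 0 when all are. With no true effect, unequal deletion raised the false positive rate to 22%. The loss of precision is a smaller matter: 4.7 points of power at 10% removed and 10.2 at 20%, from a starting value of 79.3%, with f unchanged.

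The conclusion that the exclusions are unsound rests on the text alone. Only the sizes depend on the assumptions.

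**What to change.** - In 11.3 b to f, delete the exclusions from the primary analyses and let them define the PP set only.
- In Section 17, state that the primary efficacy analysis is ITT: every randomised patient, in the arm assigned.
- Replace the wording that terminates or removes patients from the study, as far as it governs data collection. WHO score and vital status should be collected to Day 28 whatever therapy follows, unless consent is withdrawn. Deleting the analysis exclusion alone is not enough, because the text on continuing follow-up in Sections 10 and 10.2.1 is written for discharged patients and not for removed ones.
- Define treatment failure if the term is kept.
- Reconcile the dose-increase clause of 11.3b with Sections 10 and 13.2, and its reference to listed medications with Section 11.2. Which clinical rule should apply is for the sponsor and the investigators to decide.

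The cost is protocol wording, plus continued follow-up of removed patients at visits that are already scheduled.
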